7.2.3 Pregnancy

If a subject becomes pregnant during the study, in addition to reporting the pregnancy within 1 business day, a determination regarding the Janssen Ad26.CoV2.S vaccine discontinuation and subject discontinuation must be made by the sponsor-investigator in alignment with the protocol inclusion/exclusion criteria and in consultation with the Reference Safety Information (RSI).

The effect of the Janssen Ad26.CoV2.S vaccine on sperm is unknown, pregnancies in partners of male subjects exposed to the Janssen Ad26.CoV2.S vaccine will be reported by the Investigator within 1 business day of their knowledge of the event using the Serious Adverse Event Form. Depending on local legislation this may require prior consent of the partner.

Follow-up information regarding the outcome of the pregnancy and any postnatal sequelae in the infant will be required.

7.3 Reporting of Serious Adverse Events and Unanticipated Problems

When an adverse event has been identified, the study team will take appropriate action necessary to protect the study participant and then complete the Study Adverse Event Worksheet and log. The sponsor-investigator will evaluate the event and determine the necessary follow-up and reporting required.

A safety report is not considered complete until all clinical details needed to interpret the case are received.

Adverse Event Reporting Period

- (S)AEs that are related to study procedures or that are related to non-investigational Janssen products will be reported from the time a signed and dated ICF is obtained until the end of the study/early withdrawal.
 - (S)AEs not meeting the above criteria and occurring between first signing of the ICF and moment of 1st vaccination will be collected on the Medical History eCRF page as pre-existing conditions.
- All SAEs and all AEs leading to study discontinuation or discontinuation of study vaccination (regardless of the causal relationship) are to be reported from the moment of 1st vaccination until completion of the participant's last study-related procedure, which may include contact for safety follow-up. The sponsor-investigator will evaluate any safety information that is spontaneously reported by an investigator beyond the time frame specified in the protocol.
- MAAEs are to be reported for all participants from the moment of 1st vaccination until 6 months after the last vaccination, except for MAAEs leading to study discontinuation which are to be reported during the entire study.
- Special reporting situations will be recorded for each vaccination from the time of vaccination until 28 days post-vaccination.
- Solicited AEs, collected through a diary, will be recorded for each vaccination from the time of vaccination until 7 day post-vaccination.
 - If these solicited signs and symptoms are not resolved by the Day 7 contact, the subject will continue to record their daily symptoms in the diary until the Day 28 Visit or until they are resolved, whichever comes first.
- All other unsolicited AEs, whether serious or non-serious, will be recorded for each vaccination from the time of vaccination until 28 days post-vaccination. Unsolicited AEs with an onset date outside the timeframe defined above (>28 days after previous study vaccination), which are ongoing on the day of the subsequent vaccination, should be recorded as such.
- All AEs will be followed until resolution or until clinically stable.

Sponsor-Investigator Reporting to Janssen

Type of report	Timelines	How to report
Serious Adverse Event	Within 1 business day of becoming aware of the event(s)	By a secure means, as agreed by the Parties, on a Serious Adverse Event Form.
Adverse Events of Special Interest (AESI)	Within 1 business day of becoming aware of the event(s)	By a secure means, as agreed by the Parties, on a Serious Adverse Event Form.

Reports of drug exposure during pregnancy (maternal and paternal), with or without SAE.	Within 1 business day of becoming aware of the event(s)	By a secure means, as agreed by the Parties, on a Serious Adverse Event Form.
Reports of Suspected transmission of any infectious agent via administration of a J&J Product, with or without an SAE	Within 1 business day of becoming aware of the event(s)	By a secure means, as agreed by the Parties, on a Serious Adverse Event Form.
Abnormal Pregnancy Outcomes (e.g., spontaneous abortion, fetal death, stillbirth, congenital anomaly, ectopic pregnancy)	Within 1 business day of becoming aware of the event(s)	By a secure means, as agreed by the Parties, on a Serious Adverse Event Form.
Special Situation (SS), if associated with an SAE	Within 1 business day of becoming aware of the event(s)	By a secure means, as agreed by the Parties, on a Serious Adverse Event Form.
Special Situation (not associated with an SAE)	Monthly and part of scheduled data transfers	Recorded in CRF and as agreed by the Parties
Medically Attended Adverse Events (not associated with an SAE)	Monthly and part of the scheduled data transfers	Recorded in CRF and as agreed by the Parties
Product Quality Complaints	Within 3 business days of becoming aware of the event(s)	By a secure means, as agreed by the Parties.
Non-Serious Adverse Event* (*Not meeting other listed 1 business day reporting criteria e.g., special situation not associated with an SAE or MAAE)	Monthly and part of the scheduled data transfers	Recorded in CRF and as agreed by the Parties.
Follow-up information	Transmitted within the same timeframes as above i.e., if initial report was required to be submitted within 1 business day of becoming aware of follow-up information, follow-up information shall be submitted within the same timeframe.	Transmitted via same method as above i.e., if initial method of transmission was on an SAE form, follow-up information shall be transmitted in the same manner.

Study Team shall

- notify Janssen immediately in case of a suspension of recruitment or premature stop of the concerned clinical study because of a safety concern; preferably by means of a telephone contact with the Janssen Representative, alternatively by email within twenty-four (24) hours of the decision.
- provide to Janssen copies of any and all relevant extraordinary* (not including routine initial or follow-up Individual Case Safety Report submission) correspondences with health authorities and ethics committees regarding any and all serious adverse events (irrespective of the association with the Janssen Ad26.CoV2.S vaccine). Copies of such correspondence shall be provided within 24 hours of such report or correspondence being sent to applicable health authority.

*See definitions section 7.1

Contact Information	
Janssen SAE/Pregnancy Notifications	[REDACTED]
Janssen PQC:	[REDACTED]
Janssen Phone:	Contact the study assigned Janssen Trial Manager
Janssen Fax:	[REDACTED]

- Provide the batch/lot number (if available). If batch/lot number is not available, it must be documented that it is not available. Without this documentation, Janssen is required to perform two follow-up attempts to obtain the batch/lot number

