Importantly, for this trial, alterations in immunosuppression will involve changes in the dosage and sometimes type of drug administered (prednisone added when mycophenolate discontinued, for example). Drug levels for tacrolimus, cyclosporine and mycophenolate mofetil are monitored as standard of care in subjects receiving these drugs (usually monthly) and will continue to be monitored. Drug levels also will be measured at the time 0 visit in all patients in both Segment 1 and 2. However, alterations in immunosuppression will not be directed by these drug levels. They are obtained to help support patient management as needed.

We recognize that there may be an increased risk of allograft rejection or even graft loss due to the transient 6-week alteration in immunosuppression in the current study. The actual risk is unknown, but we do have clinical experience with transient immunosuppression reduction in other settings and the outcomes have been good. The DSMB will monitor for allograft rejection episodes and graft losses in this study for all groups and will examine any instance. If a rejection rate of 10% occurs at any time in the study, the study will be paused, and the protocol re-examined.

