3.6 Primary Safety Endpoints

Primary Endpoint

SAEs related to the Janssen Ad26.CoV2.S vaccine.

Secondary Endpoints

1. SAEs related to reduction in immunosuppression.
2. Any hospitalization within 2 years of randomization.
3. Microbiologically defined infectious complications.
4. Patient survival at 2 years post randomization.
5. Graft survival at 2 years post randomization.
6. Adverse events related to the Janssen Ad26.CoV2.S vaccine.
7. Adverse events related to reduction in immunosuppression (rejection, graft loss, new onset donor-specific alloantibody formation).
8. Incidence of de novo alloantibody found as SOC.
9. Occurrence and relationship of SAEs and adverse events of special interest (AESIs), medically-attended adverse events (MAAEs) (until 6 months after the last Janssen vaccination), and MAAEs leading to study discontinuation (during the entire study) for all participants.

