5.2 Treatment Regimen

5.2.1 Immunosuppression Adjustment

Immunosuppression adjustment will occur 2 weeks prior to receiving the Janssen Ad26.COV2.S vaccine and continue for 28 days receiving the Janssen Ad26.COV2.S vaccine.

Given that transplant patients are maintained on immunosuppressive regimens that vary slightly, immunosuppression adjustment will need to be somewhat individualized to the patient. However, general rules can be implemented.

Two weeks prior to receiving the Janssen Ad26.COV2.S vaccine, patients randomized to immunosuppression adjustment (or offered immunosuppression adjustment in Segment II) will be considered individually and adjustments will be made by a nephrologist with knowledge of the patient's clinical situation. General rules for adjustment are as follows:

1. For patients receiving mycophenolate mofetil (MMF) or azathioprine (AZA), a calcineurin inhibitor (CNI) (typically tacrolimus or cyclosporine), and Prednisone. Adjustment will involve stopping MMF or AZA and starting 10 mg Prednisone/day. **Note:** most patients will be in this group.
2. For patients not on MMF, but on CNI and Prednisone, the CNI dose will be decreased by 50%,
3. For patients on belatacept, which is typically taken with MMF and Prednisone, MMF will be stopped, and belatacept and Prednisone will be modified to 10 mg a day.
4. Other patients are adjusted on a case-by-case basis by the sponsor-investigator and the co-investigators—ex. Tac-mTOR inhibitor—Reduce Tac by 50%.

28 days after receiving the Janssen Ad26.COV2.S vaccine, study subjects in this arm will resume their prior doses of immunosuppression and will be followed as per protocol and as clinically indicated by the transplant team.

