6.1.2 Day -14 (+/-3 Days) Non-Responder Group Immunosuppression Change ONLY

Study team will contact the subject and document their immunosuppression medication and instruct the participant to begin their new immunosuppression medication regimen. Patient and graft status information will be recorded as well as the COVID-19 surveillance information collected.

For a subset of patients randomized to receive immunosuppression adjustment: prior to the adjustment the study team will send a kit for a local blood collection for Total Immunoglobulin levels and T-/B-cell immunophenotyping. These specimens will be shipped back to Mayo Rochester via overnight courier for testing.

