a For evaluation of any potential adverse events**b** Must have >75,000/µL to receive the Janssen Ad26.COV2.S vaccine.**c** Temperature, Height, Weight, Pulse oximetry, Blood Pressure, and Heart Rate**d** For females of childbearing potential**e** Anti-SARS-CoV-2 spike protein antibody test and anti-Nucleocapsid Antibody test will occur after consent has been obtained. The results Anti-SARS-CoV-2 spike protein antibody levels will determine into which group the subject will be placed. If randomized to receive vaccination with immunosuppression reduction, this will occur 14 days prior to vaccination (Day 0).**f** Return to previous immunosuppression medication regimen**g** Defined in Section 3.1.4**h** Will occur once at either time point**i** Subjects will be monitored for 30 minutes after vaccination to monitor for severe reactions**j** Questions regarding thrombotic events, thrombocytopenia or Guillain-Barré syndrome (Section 14.1 and 14.2). Questions regarding myocarditis and pericarditis (Section 14.7).**k** As Described in Section 6.5**l** To occur prior to vaccination on Day 0**m** MAAEs are to be reported for all participants from the moment of receiving the 1st vaccination until 6 months after the last vaccination, except for MAAEs leading to study discontinuation which are to be reported during the entire study.**n** All (S)AEs related to study procedures or non-investigational Janssen products will be reported from the time a signed and dated ICF is obtained until the end of the study/early withdrawal. All other SAEs are to be reported from the moment of vaccination until completion of the participant's last study-related procedure. AEs leading to study discontinuation or discontinuation of study vaccination (regardless of the causal relationship) are to be reported from the moment of the 1st vaccination until completion of the participant's last study-related procedure. Suspected AESIs are to be reported from the moment of vaccination until completion of the participant's last study related procedures. Special reporting situations, whether serious or non-serious, are to be recorded for each vaccination from the time of vaccination until 28 days post-vaccination. All other unsolicited AEs will be reported for each vaccination for the time of vaccination until 28 days post-vaccination.

Study Event	Day -21	Day -14	Day 0	Day 3	Day 7	Day 14	Day 28	Day 90	Day 180	1 Year	2 Years	Unscheduled Visit ^a

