*Medical and scientific judgment should be exercised in deciding whether expedited reporting is appropriate in other situations, such as important medical events that may not result in death, be life-threatening or require hospitalization but may be considered a serious adverse drug experience when, based on appropriate medical judgement, that may jeopardize the patient or subject and may require medical or surgical intervention to prevent one of the other outcomes listed in the bulleted list above. Examples of such medical events include allergic bronchospasm requiring intensive treatment in an emergency room or at home, blood dyscrasias or convulsions that do not result in hospitalization; or development of drug dependency or drug abuse or malignancy.

Per protocol problems/events that in the opinion of the sponsor-investigator may have adversely affected the rights, safety, or welfare of the subjects or others, or substantially compromised the research data will also be reported as SAE.

SAEs or events of significant interest include: thrombotic thrombocytopenia syndrome, Guillan Barre Syndrome, myocarditis, pericarditis, acute rejection, de novo DSA or graft loss associated with immunosuppression adjustment, readmission to the hospital for any reason. These events and their sequelae will be followed for the duration of the study in participants who received the Janssen Ad26.COV2.s vaccine. AEs that are deemed related to the Janssen Ad26.COV2.s vaccine will be followed for day 28 after vaccination.

All adverse events that do not meet any of the criteria for serious, should be regarded as **non-serious adverse events**.

Unanticipated Problems Involving Risk to Subjects or Others (UPIRTSO)

Any unanticipated problem or adverse event that meets the following three criteria:

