7.3.1 Sponsor-Investigator reporting: notifying the Mayo IRB

The sponsor-investigator will report to the Mayo IRB any UPIRTSOs and Non-UPIRTSOs according to the Mayo IRB Policy and Procedures.

Information collected on the adverse event worksheet and entered in the research database:

- Subject's name
- Medical record number
- Disease/histology (if applicable)
- The date the adverse event occurred
- Description of the adverse event
- Relationship of the adverse event to the research (drug, procedure, or intervention*)
- If the adverse event was expected
- The severity of the adverse event (use a table to define severity scale 1-5**)
- If any intervention was necessary
- Resolution: (was the incident resolved spontaneously, or after discontinuing treatment)
- Date of Resolution:

The sponsor-investigator will review all adverse event reports to determine if specific reports need to be made to the IRB and FDA. The sponsor-investigator will sign and date the adverse event report when it is reviewed. For this protocol, only directly related SAEs/UPIRTSOs will be reported to the IRB.

Consider the use of a table to define the Relationship of an Event to the Research and the severity of each event.

Assessment of Causality

The relationship of an AE to the Janssen Ad26.CoV2.S vaccine is a clinical decision by the sponsor-investigator (S-I) based on all available information at the time of the completion of the CRF and is graded as follows:

1. Not Related: a reaction for which sufficient information exists to indicate the etiology is unrelated to the study drug; the subject did not receive the study medication or the temporal sequence of the AE onset relative to administration of the Janssen Ad26.CoV2.S vaccine is not reasonable or the event is clearly related to other factors such as the subject's clinical state, therapeutic intervention or concomitant therapy. By definition, all solicited AEs at the injection site (local) will be considered related to the Janssen Ad26.CoV2.S vaccine administration.
2. Unlikely: a clinical event, including laboratory test abnormality, with a temporal relationship to drug administration which makes a causal relationship improbable and in which other drugs, chemicals, or underlying disease provide plausible explanations.

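### In Segment I, general adverse event reporting starts 14 days after the randomized immunosuppression adjustment, so early events can be misfiled and undosed participants lost

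*Combined protocol and SAP*

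**What the plan says.** **Timing of the intervention.** Section 5.2.1: "Immunosuppression adjustment will occur 2 weeks prior to receiving the Janssen Ad26.COV2.S vaccine and continue for 28 days" after the dose, when prior doses are resumed. Section 1.5.9 calls this a "transient 6-week alteration in immunosuppression in the current study". The starting visit is Section 6.1.2, "Day -14 (+/-3 Days) Non-Responder Group Immunosuppression Change ONLY".

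**Timing of reporting.** Section 7.3 has two starting points. (S)AEs related to study procedures (or to non-investigational Janssen products) are reported from signed consent. All SAEs, MAAEs and unsolicited AEs are otherwise reported from vaccination, and Section 7.2.2 does the same for suspected AESIs. An (S)AE outside the first category and "occurring between first signing of the ICF and moment of 1st vaccination will be collected on the Medical History eCRF page as pre-existing conditions". The footnotes to Schedules 2B and 2C in Section 6.6 repeat the starting points.

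**What the trial wants to know.** Secondary objective 3 (Section 2) is safety with or without immunosuppression adjustment. The secondary safety endpoints in Section 3.6 include SAEs related to the reduction and "Adverse events related to reduction in immunosuppression (rejection, graft loss, new onset donor-specific alloantibody formation". Hospitalization, patient survival and graft survival are counted from randomization.

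**Related rules.** Section 7.2 requires every adverse event in the study period to be recorded. Section 7.1 names acute rejection, de novo DSA and graft loss associated with adjustment as events of significant interest, then says: "These events and their sequelae will be followed for the duration of the study in participants who received the Janssen Ad26.COV2.s vaccine". Section 7.3.1 introduces its graded causality scale with: "The relationship of an AE to the Janssen Ad26.CoV2.S vaccine is a clinical decision by the sponsor-investigator".

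**The concern.** The reporting clock is built around the vaccine, which both randomized arms receive. What is randomized is the adjustment, and it starts two weeks before the clock does. An admission or rejection in those two weeks begins after the intervention, yet it can be filed as if it came before the study.

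Whether it is filed that way depends on an open-label judgement of relatedness to study procedures. The protocol does not say whether the adjustment is one, and the only graded causality scale concerns the vaccine. A harms comparison between arms is weaker when events enter it through a causality screen.

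Loss of participants who are never dosed may also be related to outcome. Section 4.5 delays vaccination for significant acute illness or for a further change in immunosuppression. An event in the gap could therefore be the reason that the participant is not dosed.

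**Working it through.** **1. The plan's own duration.** Inputs from Section 5.2.1: 14 days before and 28 days after vaccination. 14 + 28 = 42 days, and 42 / 7 = 6.0 weeks. This reproduces the 6 weeks in Section 1.5.9.

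**2. Share before general reporting starts.** 14 / 42 = 33.3%. For the 150 participants planned in the adjusted arm: 150 × 14 = 2,100 of 150 × 42 = 6,300 planned exposure days.

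**3. Effect of the visit windows** (start Day −14 ± 3, vaccination −4/+1, end Day 28 ± 7 counted from the actual dose).
- Shortest gap: Day −11 to Day −4 = 7 days. Smallest share: 7 / (7 + 35) = 16.7%.
- Longest gap: Day −17 to Day +1 = 18 days. Largest share: 18 / (18 + 21) = 46.2%.

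**4. An adjusted-arm admission or rejection on Day −5, traced through the rules.**

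| Case | Section 7.3 | Other provisions |
|---|---|---|
| Judged related to study procedures | Reported, from consent | Depends on an undefined term |
| Not so judged; later dosed | Medical History, pre-existing | Section 6.1.3: nephrology consult, graft status, and the Section 14.5 questionnaire, which asks about hospitalization and rejection |
| Not so judged; never dosed | Medical History, pre-existing | Outside Section 7.1 follow-up and the all-treated population (Section 6.9). Section 4.5 discontinues participants not dosed within the screening window. Sections 4.4.1 and 4.4.2 stop data acquisition after withdrawal |

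In the second row the event is known but misclassified. In the third it can disappear, and so can later graft or patient survival, although Section 3.6 counts both from randomization.

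**5. Comparator arm.** Section 5.2.2 vaccinates it 2 weeks after randomization, under the same Section 7.3 rule. Its unreported period is similar in length but contains no exposure to adjustment.

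**6. Segment II.** Adjustment starts on Day 42 and the second dose is on Day 56. SAEs and MAAEs have been reportable since the first dose. Unsolicited AE collection stops 28 days after that dose, and events ongoing at the second dose are recorded. What is missed in the adjusted period is therefore non-serious AEs on Days 42–56 that resolve before the second dose.

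**7. Illustration only.** If rejections were spread evenly over the 42 days in 150 participants, a 10% rate would give 15, of which 15 × 14/42 = 5 fall before dosing. A 5% rate would give 2.5 of 7.5. The documents give neither an expected rate for this trial nor a time pattern; 10% is the pause threshold in Section 1.5.9.

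**The case against.** The strongest defence is the exception in Section 7.3. The adjustment endpoints in Section 3.6 are defined as events related to the reduction. If a protocol-mandated adjustment is a study procedure, those events are reportable from consent. The worksheet in Section 7.3.1 also asks for the relationship to the drug, procedure or intervention, so relatedness to the adjustment can be recorded. Graft status is taken at Day −14 and Day 0, and biopsy and laboratory results are in the medical record (Section 3.7). The primary endpoint (Day 28 antibody) and the primary safety endpoint (vaccine-related SAEs) are untouched.

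Most of this stands, and it limits the point. It does not remove it. The exception works only if the term is defined. It does nothing for hospitalization, which Section 3.6 counts from randomization whatever the cause. The Day 0 routes do not help a participant who never reaches Day 0.

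A reader might infer four stronger things that the documents do not support:
- *A third of the adjustment's harms become medical history.* One third is exposure time. Events judged related to study procedures are excepted.
- *Only the adjusted arm is affected.* The recording rule applies to both arms; only the exposure differs.
- *The DSMB's rejection count is too low.* Section 1.5.9 has the DSMB monitor rejection and graft loss in all groups and does not tie that count to the Section 7.3 clock.
- *Five of 15 rejections will be missed.* That figure rests on an assumed rate and even timing. It counts rejections before dosing, and only those not judged related to study procedures would be misfiled. Section 1.5.9 reports clinical rejection below 10% in the sites' experience with usually much longer reductions.

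**Conclusion.** The mismatch is real and follows from a stated rule. At nominal timing, 33% of planned Segment I adjustment exposure precedes general reporting, which is 7 to 18 days within the visit windows. Section 7.3 conflicts with Section 3.6 and, at face value, with Section 7.2; Section 7.1 narrows follow-up further.

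For participants who reach Day 0 the consequence is mainly misclassification. For randomized participants who are never dosed it can be loss of data. Harm caused by adjustment in the gap can arise only in the adjusted arm, so misfiling or losing it would favour that arm. The documents do not allow the number of events to be estimated.

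This should be fixed as a cheap improvement to the safety comparison. It does not threaten the primary analysis. The conclusion assumes that sites apply Section 7.3 as written and that the status of the adjustment as a study procedure stays undefined.

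**What to change.** 1. In Section 7.3 and Schedules 2B and 2C, start collection of AEs, SAEs, MAAEs, rejection, DSA and graft loss at randomization in both randomized arms, regardless of causality or later dosing.
2. State that the adjustment counts as a study procedure or intervention when relatedness is judged.
3. In Section 7.1, extend follow-up of the events of significant interest to all randomized or vaccinated participants.
4. In Sections 4.4 and 4.5, provide for continued collection of these safety outcomes, with consent, in randomized participants who are not dosed.
5. In Sections 6.8 and 6.9, report these harms by randomized arm in the all-randomized population, from randomization.
6. In Segment II, start non-serious AE collection when the adjustment starts.
7. Reconcile Section 7.3 with Sections 3.6, 7.1 and 7.2.

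The cost is protocol and eCRF wording, plus two to three weeks of extra AE entry for about 300 participants. Participants who go on to vaccination need no new visit: the adjusted arm already has a Day −14 contact, and both arms have a Day 0 visit.
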